## 1.0 Study Summary

Investigational Agent(s) (Drugs or Devices)	Roger Select (Remote microphone manufactured by Phonak, subsidiary of Sonova)
IND / IDE / HDE #	IDE Exempt: This is a legally marketed device and will be used in accordance with its labeling.
Indicate Special Population(s)	 Children  Children who are wards of the state  Adults Unable to Consent  Cognitively Impaired Adults  Neonates of Uncertain Viability  Pregnant Women  Prisoners (or other detained/paroled individuals)  Students/Employees
Sample Size	40
Funding Source	Sonova
Indicate the type of consent to be obtained	 Written  Verbal/Waiver of Documentation of Informed Consent  Waiver of HIPAA Authorization  Waiver/Alteration of Consent Process
Site	 Lead Site (For A Multiple Site Research Study)  Data Coordinating Center (DCC)
Research Related Radiation Exposure	 Yes  No
DSMB / DMC / IDMC	 Yes  No

## 2.0 Objectives:

Despite improvements in digital hearing aid technology, many individuals with hearing loss continue to report difficulty understanding speech in challenging listening environments. Remote microphones have been shown to provide benefit in many of the most common challenging listening environments: distant speakers, background noise and reverberation. Despite demonstrated benefit, there is a low rate of remote microphone use amongst adults with hearing impairment. One reason for low uptake may be an uncertainty amongst hearing healthcare providers and potential users regarding expected clinically relevant benefit. This clinical trial, funded by Sonova, will attempt the following:

1. To describe the range of Roger remote microphone benefit among adults with mild-to-moderate sensorineural hearing loss
2. To determine specific individual factors beyond the audiogram that are associated with greater Roger remote microphone benefit.

## 3.0 Background / Literature Review / Rationale for the study:

Even when wearing well-fit hearing aids, many individuals with hearing loss continue to report difficulty communicating in background noise is one of the most common

complaints of individuals with hearing loss. Directional microphones can improve speech perception in noise, but often fail to provide benefit in cases where the talker is distant from the listener, where there are multiple or moving noise sources, or in reverberation. Digital noise reduction may reduce listening effort and improve listening comfort but has minimal effect on speech perception.

Placing the microphone in close proximity to the talker reduces the effective distance between speaker and listener, compensating for the effects of background noise and reverberation on the target signal. Use of a remote microphone can significantly improve signal-to-noise ratio (SNR), thereby improving speech perception in noise and at a distance. Recent studies demonstrated that remote-microphone devices that utilize adaptive digital technology (i.e., Roger) provide significantly more benefit for speech understanding in noise than non-adaptive remote microphones. Those advantages are likely related to the adaptive nature of the device, whereby the microphone gain varies according to the level of noise in the environment. In addition, interference is reduced via transmission of short digital bursts (160  $\mu$ s) across a range of channels (2.4-2.4835 GHz). Further, the ability to utilize the hearing aids' onboard directional microphones in conjunction with a remote microphone gives listeners the benefits of remote microphone use without sacrificing nearfield intelligibility. The Roger system has also been shown to improve cell phone communication amongst cochlear implant patients.

Despite demonstrated advantages, use of remote microphone assistive devices among adults is low. In a recent study of listeners with severe hearing loss—a group which has substantial difficulty communicating in background noise and is likely to receive significant benefits from remote-microphone devices—less than 10% reported use of a remote microphone. While cost may be a barrier for some users, even when such systems are available for free (as in the Veterans Administration), use is still low. *One reason may be uncertainty among both providers and potential users as to expected benefit for a given listener.* For example, Wolfe et al. 2015 found significant improvements in objective speech recognition on average, but with a wide range of benefit (from 10% to 60% improvement across individual participants). That study also suggested that individual factors may affect remote microphone benefit, in that the magnitude of improved recognition was correlated with the ability to use spatial cues to improve recognition.

## 4.0 Study Endpoints

Primary Endpoint: Benefit from use of a remote microphone.

1. Abbreviated Profile of Hearing Aid Benefit (APHAB): This is a measure of hearing aid benefit that is standard in clinical practice. Participants will complete this questionnaire to compare perceived aided benefit with hearing aid alone vs hearing aid+ remote microphone.

Secondary Endpoints: In order to build a better profile of patients who may benefit from a remote microphone, several measures of hearing ability, manual dexterity, personality, and social activity are included.

2. Audiometric evaluation including hearing and health history, air and bone condition testing, measurement of loudness discomfort level and real-ear assessment of current hearing aids. These are all standard clinical assessments.
3. MoCA test: The Montreal Cognitive assessment is a cognitive screening test designed to detect mild cognitive impairment. It requires approximately 10 minutes and assesses short-term recall, visuospatial abilities, executive function, attention, working memory, language, and orientation to time and place.
4. Practical Hearing Aid Skills Test-Revised (PHAST-R)- will be used to ensure participants are able to use the trial devices
5. Unaided and Aided speech in noise testing: This is a standard clinical measure of an individual's ability to hearing and understand speech in background noise.
6. Speech, Spatial, and Quality of Hearing Scale (SSQ) pre- and post- Roger use: Evaluates an individual's perceptions of their hearing abilities in a variety of every day scenarios.
7. Acceptable Noise Level (ANL): This test has been shown to be correlated with successful hearing aid use.
8. LiSN-S: Spatial auditory information assessment. This test has been shown to correlate with successful assistive listening device use.
9. Level of social activity, using the HRS Activities and Time Use subscale
10. Personality, using the Positive and Negative Affectivity Scale (PANAS) and International Personality Item Pool (IPIP). Personality has been shown to be related to successful hearing aid use.
11. Self-efficacy, using the Generalized Self-Efficacy Scale. Self-efficacy is an individual's belief in his/her ability to achieve a goal and has been linked with hearing device satisfaction.
12. Working memory will be measured via the short version of the Reading Span Test. Working memory is the ability to rapidly process and store information and has been associated with speech-in-noise recognition. In addition, listeners with low working memory are thought to expend greater listening effort to understand speech. It has been suggested that listeners with low working memory will receive greater benefit from remote microphone technology.
13. Nine-hole peg test will be used to evaluate participants' dexterity.

## 5.0 Study Investigational Agent

The Roger Select is a remote microphone manufactured by Phonak, a subsidiary of Sonova (the funding group). To minimize confounding factors, participants will also be fit the same model and make of hearing aids (Phonak Marvel 90) for the duration of the trial. Both the Roger Select and the hearing aids are legally marketed devices currently available to consumers and will be used in this trial in accordance with its labeling, making this an IDE exempt regulation (21 CFR 812).

Only current hearing aid users will be recruited for this trial and a licensed audiologist will fit the hearing aids and remote microphones. Devices will be programmed to standard clinical targets and verified using real ear measures, a standard clinical procedure.

Devices are being provided by the manufacturer, Phonak. All hearing aids and their accessories come with unique serial numbers. Upon receiving the devices, they will be evaluated for good function and serial numbers will be noted in the device log. We will note in the log when and to whom (using participant ID number) each individual device is dispensed. When a participant returns a device this will be tracked in the log, as well as when we return to the manufacturer.

## 6.0 Procedures Involved:

Approach: The trial will use a within-subjects design consisting: 1)Baseline assessments (see assessments), 2) Being fit with trial hearing aids for a two week adjustment period, 3) Roger connect fitting appointment, 3) Approximately four-week trial period of Roger use in the participant's everyday environment(s), 4) Final visit with outcome measures.

Participants whose hearing loss qualifies them for a dome mold fitting (non-custom) will start their trial the same day as their eligibility assessment. Participants whose hearing loss or ear structure requires a custom mold fitting will have earmold impressions taken at their eligibility assessment and then be fit with the trial devices after the custom earmold has arrived back in the lab, usually about one to two weeks later. During an earmold impression the ear is visually inspected with an otoscope (magnifying scope with light). A cotton or foam block and soft impression material are placed in the ear and sets for approximately 3 minutes. The resulting impression is used to order an earmold for later testing. This is a standard clinical procedure.

A licensed clinical audiologist will perform the assessments, fitting and counseling of hearing aids and Roger system, and conduct the outcome measures. To ensure appropriate fit and use by the participants, there will be a follow-up one week after receiving the Roger. During this appointment participants will be evaluated, and their hearing aid logging will be checked for compliance.

Hearing aid/Roger fitting: Trial hearing aids and clinically-appropriate earmolds or domes will be provided by Sonova at no charge to the participants for the duration of the trial. The Marvel 90 hearing aids are Phonak's advanced technology level and to provide datalogging via 7 base programs. Aids will be set to NAL-NL2 targets using probe microphone measurements. Directional microphones will be enabled and verified via probe-microphone testing. Roger will be verified via probe-microphone testing, following clinical best practice. Appropriate hearing aid adjustments (as judged by the study audiologist) will be permitted to provide acceptable sound quality and loudness. Final REARs will be recorded. Participants will be fit with the trial hearing aids and wear them for two weeks prior to receiving the Roger device. This is to allow participants to adjust to the sound quality of a new pair of hearing aids and ensure that measured differences are due to Roger use and not the newer hearing aids. The study audiologist will instruct participants regarding hearing aid and Roger device use. PHAST-R and a Roger competency questionnaire (to be developed with input from Phonak) will be used to document understanding of device function at the fitting and one-week follow-up appointments. Participants will then wear the hearing aids and use the Roger system for 1

month in their everyday listening environments. At the completion of the trial, participants will return to the lab for outcome assessments and to provide spontaneous feedback regarding their experiences. Hearing aids will be returned to the study site following completion of the trial.

## 7.0 Sharing Results with Participants

An audiologist will share and review the hearing test results with participants. They will also be given a copy of the test results if they so choose.

## 8.0 Study Timelines

Individual Participant Timeline: Active study time for participants will be about 6 weeks, during which they will visit the lab at least four times: baseline+fitting of hearing aids, fitting of Roger, one-week follow-up, and final visit. Participants who require an earmold will require a two separate visits for baseline and hearing aid fitting. For these participants, there will be a one to two-week delay between their baseline and hearing aid fitting appointment while the earmold is manufactured. Visits will typically take 1-2 hours. Some participants who require more counseling or breaks than is typical may find their visit durations last longer. Other participants may need to visit the lab for more appointments to ensure good physical and acoustic fit. Appointments will also be scheduled at participant's convenience, so the duration of study stages (e.g. adjustment period) may vary slightly to accommodate an individual's scheduling needs.

Overall Study Timeline: Once enrollment begins, we hope to enroll approximately 2-3 participants a week. Enrollment should be reached in 10 to 14 weeks. Study activities should then complete 6-8 weeks after that. Estimated data collection period will be 16-20 weeks, with the possibility of an extension should recruitment prove slower than anticipated. Primary data analyses will take place immediately on completion of data collection.

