## **10.0 Sample Size:**

Northwestern plans to enroll 40 total participants.

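### Does the recruitment forecast in section 8.0 put the sample size of 40 at risk?

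*Protocol*

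**What the plan says.** Three statements in the protocol bear on this point.

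- **Target.** Section 10.0 states: "Northwestern plans to enroll 40 total participants". The summary in section 1.0 gives the same number. Neither place attaches a date or a duration.
- **Rate and enrollment period.** Section 8.0 says: "Once enrollment begins, we hope to enroll approximately 2-3 participants a week. Enrollment should be reached in 10 to 14 weeks".
- **Completion and total.** Section 8.0 continues: "Study activities should then complete 6-8 weeks after that". It then gives the overall period: "Estimated data collection period will be 16-20 weeks, with the possibility of an extension should recruitment prove slower than anticipated". For one person, the same section says "Active study time for participants will be about 6 weeks", and those who need an earmold wait one to two weeks more.

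Primary analysis is to follow once data collection is complete. It is not tied to a calendar week.

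**The concern.** Rate, duration and sample size are linked by one multiplication, and the three stated values do not multiply out over most of their ranges. Nor do the two stated phases add up to the stated total at the upper end. The extension clause seems not to help, because it is offered for recruitment slower than expected, whereas the shortfall appears at the expected rate itself.

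If someone treated the forecast as a deadline and stopped at week 14 or week 20, the study could end with well under 40 participants. Both aims in section 2.0 would then rest on fewer people: describing the range of benefit, and finding the individual factors associated with it.

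**Working it through.** **Inputs.** N = 40 (sections 1.0 and 10.0). From section 8.0: rate r = 2 to 3 a week, enrollment 10-14 weeks, completion f = 6-8 weeks after enrollment ends, total 16-20 weeks. The value 2.5 a week is simply the midpoint.

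**The plan's own total.** 10 + 6 = 16 and 14 + 6 = 20 reproduce the stated 16-20 weeks. So the total matches if 6 weeks is used at both ends, which is the stated active time per participant. With the stated 6-8 weeks, the upper end is 14 + 8 = 22. The discrepancy is two weeks.

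**Participants enrolled = rate × weeks.**

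| Rate per week | 10 weeks | 12 weeks | 14 weeks |
|---|---|---|---|
| 2 | 20 | 24 | 28 |
| 2.5 | 25 | 30 | 35 |
| 3 | 30 | 36 | 42 |

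One of the nine cells reaches 40. The central cell, 30, is (40 − 30)/40 = 25% short.

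**Rate needed = 40 / weeks.** 40/10 = 4.0, 40/12 = 3.33 and 40/14 = 2.86 a week. Only the last lies within 2 to 3.

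**Time needed = 40 / rate, then plus 6 to 8 weeks.**

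| Rate per week | Weeks to enroll 40 | Total weeks |
|---|---|---|
| 2 | 20 | 26-28 |
| 2.5 | 16 | 22-24 |
| 3 | 13.3 | 19.3-21.3 |

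**Can all the figures hold at once?** Yes, in a corner. At 3 a week, enrollment takes 13.3 weeks (inside 10-14), and 6 more weeks give 19.3 (inside 16-20). With a 6-week completion, the slowest rate that still finishes by week 20 is 40/(20 − 6) = 2.86 a week.

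**Does any rule turn the forecast into a deadline?** None is stated. The rate is expressed as a hope and an approximation, and the total as an estimate that may be extended. The enrollment sentence treats the target as the end point and the weeks as a prediction of when it is met.

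**The case for a change.** The strongest case for a correction is that hedging excuses scatter around a coherent plan, and this plan is not coherent at its centre. The 10-week end cannot be met at any rate in the stated range. Pairing the fast rate with the short period and the slow rate with the long one gives 3 × 10 = 30 and 2 × 14 = 28, so the forecast describes a study of about 30 rather than 40. The corner where everything agrees is also fragile. If the last person enrolled needs an earmold, completion takes at least 6 + 1 = 7 weeks, and even 3 a week then gives 13.3 + 7 = 20.3 weeks. The extension clause is worded for a different event. Staffing and device supply may be planned from these weeks, and correcting a few figures costs almost nothing.

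The arithmetic in this stands, and so does the remark about the wording of the extension clause. The step from a wrong forecast to a smaller sample does not stand. It needs a stopping date that the protocol does not contain. The number 40 appears in two places without condition, and the extension clause, however it is worded, shows that the calendar is meant to give way to recruitment. Asking that enrollment end at 40 participants rather than at a date would repair a rule that is not there. The largest gap that can be drawn from the figures, 28 against 20 weeks, also pairs the slowest rate with the longest completion. At the middle rate the overrun is 2 to 4 weeks.

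**Conclusion.** Section 8.0 contains a clerical planning slip. The stated rate reaches 40 within 14 weeks only at 2.86 a week or more, and the phases add to 16-22 weeks rather than 16-20. Ranges consistent with the stated rate would be about 13-20 weeks for enrollment and 19-28 weeks for data collection. Alternatively, a rate of about 3 to 4 a week would match the stated enrollment period (40/4 = 10 and 40/3 = 13.3 weeks). The document does not show which figure slipped.

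No change to the plan follows. At the middle rate the likely effect is a study that runs 2 to 4 weeks past its estimate, in a single-site, within-subjects design where each person takes part for about 6 weeks. The sample size, eligibility, endpoints and analysis do not depend on the forecast, so restating it would alter nothing that the trial does or concludes.

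This rests on one assumption: that the team recruits to the stated 40 and uses the extension if it needs to, as the text implies. If enrollment were in fact closed on a calendar date, the shortfall would become real, but the protocol gives no sign of that.

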## 9.0 Inclusion and Exclusion Criteria:

### Inclusion criteria:

1. Adults age 18+years
2. Speak English as their primary language
3. Normal or corrected-to-normal vision
4. Sensorineural hearing loss with pure-tone thresholds 20-85 dB HL at octave frequencies between 500 and 3000 Hz

Current hearing aid wearer with at least 3 months of experience

### Exclusion criteria:

1. Clinically significant unstable or progressive medical conditions, or conditions which, in the opinion of the investigator places the participant at unacceptable risk if he or she were to participate in the study
2. Participants who do not pass a cognitive screening test (e.g., MoCA, MMSE or DRS-2)

3. Significant history of otologic or neurologic disorders
4. Conductive hearing loss pathology or fluctuating hearing loss

No special populations will be enrolled in the study (e.g.: Adults unable to consent, minors, pregnant women or prisoners).

## **10.0 Sample Size:**

Northwestern plans to enroll 40 total participants.

## **11.0 Research Locations:**

All study tasks will take place in the Hearing Aid Lab, Northwestern's Center for Audiology, Speech, Language and Learning, or the School of Communications office suite in Abbot Hall located on Northwestern's downtown campus.

When testing in the Hearing Aid Lab, Frances Searle building room 1-451, we will either use the sound booth or lab space. All hearing related tasks take place in a sound booth which is a sound treated 8'x 8' room within the larger lab space. When taking histories or cognitive measures we will use the office space located within the lab or an additional nearby (i.e. same building) testing room. The additional test room is only used if participant confidentiality can be maintained (i.e. conversation is not audible to those outside the room). When using the Center for Audiology, Speech, Language and Learning all tasks will take place in a sound proof booth, in a clinical Hearing Aid fit room, or the virtual sound environment (ViSoR). ViSoR is a 16' by 14' by 9' space capable of simulating the acoustics and background noise properties of any environment by using an array of speakers. When using the Abbot Hall location, testing will take place in the testing suite #1700 which has been sound treated and is currently in use for clinical studies. Participants will be given the option to schedule appointments at the location of their choosing except for the final appointment. The final appointment must take place at the Evanston location due to equipment requirements.

## **12.0 Multiple sites:**

N/A

## **13.0 Reliance Agreements/Single IRB:**

N/A

## **14.0 Incomplete Disclosure or Deception:**

N/A

## **15.0 Recruitment Methods:**

Participants will be recruited from a variety of sources.

1. A within-laboratory participant pool of prospective participants aged 18 to 96 years has been established by the PI.
2. Flyers posted around Northwestern University's campus, off-campus community bulletin boards, and relevant online communities/message boards.
3. Northwestern University Audiology Clinic. We plan to recruit older listeners with hearing loss who seek clinical care to obtain new hearing aids. Clinicians will receive a set of participant criteria. All patients seen for clinic appointments that meet the criteria and plan to be fit with one of the hearing aids predetermined to be of relevance to this study will be offered participation in the study.
4. Local senior centers, and local chapters of the Hearing Loss Association (HLAA).
5. Communication Research Registry: The Communication Research Registry is a confidential database for individuals and families who would like to continue participating in research housed within Northwestern University's School of Communication. These individuals sign up with the intention of being contacted for various research studies centered on human communication and development.
6. Local newspaper advertisements.

## **16.0 Consent Process:**

Prior to enrollment, potential participants will have a hearing and cognitive test with authorization by a screening consent form. These tests will allow us to exclude potential participants from enrolling in the study who are ineligible based upon their hearing or cognitive status. These 45-minute tests are built into the study design of visit 1 tasks and do not require additional visits. If a participant is not eligible to participate based upon the screening consent, they can authorize future contact with the consent's optional element and authorize the lab to retain the screening audiogram. If participant is eligible based upon their screening results, they will be enrolled in the study with separate consent. Some participants recruited from our participant database may have already passed the eligibility screening assessments and indicated their wish to be considered for other studies may be contacted. Should these participants decide this study is of interest to them, they will not need to repeat these measures and will proceed to the full consent form. All participants will provide their consent to study procedures to the investigator or her research assistants. This process will take place in the Hearing Aid Laboratory, prior to any research procedure taking place. All consent forms are stored in a locked file cabinet drawer within the Hearing Aid lab (a locked laboratory). An unlimited amount of time will be provided to the participant to ensure they have adequately reviewed the consent form and all questions have been addressed by study staff.

Following the participant's opportunity to read the consent document, study staff will review each section with participant to clarify the study or any procedure and ensure understanding. Additionally, consent forms may be provided to a potential research participant before a study visit is scheduled so they may take extra time to review before committing to participation. All participants will receive a copy of their signed consent form. We will give participants the option of being audio and/or video recorded during this experiment (for both screening and data collection). The objective of this recording is to be able to have internal lab staff reliability discussions to ensure test reliability and accuracy. When recorded, participant anonymity will be maintained (i.e. name is not being said, face is not recorded, hands are being recorded if possible). Participants will

document on the consent forms whether or not they agree to being recorded, or if recording is not applicable for a specific experiment. Recordings will be kept and used for lab staff only and will be destroyed once data analysis is complete.

